8.4 Serious Adverse Events

8.4.1 Serious Adverse Event Definition

Serious AEs are defined as follows:

An event is defined a serious adverse event if it:	Guidance
results in death	Any event resulting in a fatal outcome must be fully documented and reported, including deaths occurring within 4 weeks after the treatment ends and irrespective of the causal relationship to the IMP. The death of a subject enrolled in a trial is per se not an event, but an outcome.
is life-threatening	The term life-threatening refers to an AE in which the subject was at immediate risk of death at the time of the event. It does not refer to an event, which may have caused death if it were more severe.
requires in-patient hospitalization or prolongation of existing hospitalization	The term hospitalization means that the subject was admitted to hospital or that existing hospitalization was extended as a result of an event. Hospitalization describes a period of at least 24 hours. Overnight stay for observation, stay at emergency room, or treatment on an outpatient basis do not constitute a hospitalization. However, medical judgment must always be exercised and, when in doubt the case should be considered serious (i.e., if case fulfils the criterion for a medically important event). Hospitalizations for administrative or social purposes do not constitute SAEs. Hospital admissions and/or surgical operations planned before trial inclusion are not considered AEs, if the illness or disease existed before the subject was enrolled in the trial, provided that the condition did not deteriorate during the trial.
results in persistent or significant disability/incapacity	Disability/incapacity means a substantial disruption of a person's ability to conduct normal life functions. In doubt, the decision should be left to medical judgment by the investigator.
is a congenital anomaly/birth defect	Congenital anomaly/birth defect observed in any offspring of the subject conceived during treatment with the IMP.
is an important medical event	
Important medical events are events that may not be immediately life-threatening or result in death or hospitalization but may jeopardize the subject or may require intervention to prevent 1 of the other outcomes listed in the definition above. Examples of important medical events include AEs that suggest a significant hazard, contraindication or precaution, occurrence of malignancy, or development of drug dependency or drug abuse. Medical and scientific judgment should be exercised in deciding whether events qualify as medically important.
 
Important medical events include any suspected transmission of an infectious agent via a medicinal product. Any organism virus or infectious particle (e.g., prion protein transmitting transmissible spongiform encephalopathy), pathogenic or non-pathogenic, is considered an infectious agent. A transmission of an infectious agent may be suspected from clinical symptoms or laboratory findings indicating an infection in a subject exposed to a medicinal product.

8.4.2 Collection, Recording and Reporting of Serious Adverse Events

SAE Reporting by the Investigator

All SAEs must be reported **immediately** to Global Pharmacovigilance at Ferring Pharmaceuticals as soon as it becomes known to the investigator and not later than within 24 hours of his/her knowledge of the occurrence of an SAE. The investigator is responsible for submitting the completed paper SAE report form with the fullest possible details **within 3 calendar days** of his/her knowledge of the SAE.

The SAE must be included in the eCRF system. In addition, a paper SAE report must be completed and submitted according to the instructions provided on the form and sent to Global Pharmacovigilance at Ferring Pharmaceuticals using the contact details below.

Global Pharmacovigilance, Ferring Pharmaceuticals A/S

E-mail: [REDACTED]

Fax: [REDACTED]

eCRF information regarding demographics, AEs, medical history, and concomitant medication is **mandatory** for initial reports and for follow-up reports if any changes have been made since the initial report.

Additional information relevant to the SAE, such as hospital records, results from investigations (e.g., laboratory parameters that are not already uploaded in the eCRF, invasive procedures, scans, x-rays, and autopsy results) can be faxed or scanned and e-mailed to Ferring Global Pharmacovigilance using the contact details in the section above. In any case this information must be supplied by the investigator upon request from Ferring. On any copies provided, such details such as subject's name, address, and hospital ID number should be concealed, and subject number should be provided instead.

The investigator will supply Ferring and the IEC/IRB with any additional requested information, such as results of post-mortem examinations and hospital records.

Expedited Reporting by Ferring

Ferring will report all AEs that are **serious, unexpected, and with a reasonable possible causality to the IMP** as judged by either the investigator or Ferring to the relevant parties within the stipulated timelines. The expectedness of events will be assessed by Ferring according to the Investigator's Brochure.

SAEs will be considered reportable regardless of whether the IMP was used in accordance with the provisions in the protocol, Investigator's Brochure, and labelling.

8.5 Follow-up of Adverse Events and Serious Adverse Events

8.5.1 Follow-up of Adverse Events with Onset during the Trial

During the trial, the investigator must follow each AE until it is resolved or until the medical condition of the subject is stable.

After the subject's last visit, the investigator must follow-up on any AE classified as serious or considered to have a reasonable possible causality to the IMP until it is resolved or until the medical condition of the subject is stable. All such relevant follow-up information must be reported to Ferring. If the event is a chronic condition, the investigator and Ferring may agree that further follow-up is not required.

8.5.2 Collection of Serious Adverse Events with Onset after Last Trial Visit

If an investigator becomes aware of an SAE after the subject's last visit, and he/she assesses the SAE to have a reasonable possible causality to the IMP, the case will have to be reported to Ferring, regardless how long after the end of the trial this takes place.

9 STATISTICAL METHODS

All analyses will be detailed in a subsequent statistical analysis plan.

9.1 Determination of Sample Size

The true remission rates at Month 6 for mesalamine 2 g extended release granules (sachet) and placebo regimens were assumed as 68% and 49%, respectively, based on The Mesalamine Study Group (1996) (3), Hawkey et al (1997) (4), and Apriso™ package insert (2009). (5) Under these assumptions, a sample size of 120 randomized subjects per group will provide at least 85% power to detect a statistically significant treatment group difference in the remission rate at a two-sided 0.05 significance level using the chi-square test. To maintain the power for the primary efficacy analysis that excludes subjects who are rolled over from the placebo group in the 000174 trial via Pathway 1, approximately 260 subjects will be randomized.

9.2 Subject Disposition

The number of screened subjects will be summarized, and for subjects not randomized, the primary reason for exclusion from randomization will be summarized.

The number and percentage of subjects who are randomized, are treated with IMP, prematurely discontinued, and completed the trial will be summarized with the reasons for premature discontinuations.

The time to discontinuation will be summarized by the Kaplan-Meier estimates, and the treatment group difference will be tested by the log-rank test. In addition, reason-specific discontinuation will be summarized by the cumulative incidence estimates.

9.3 Protocol Deviations

The following protocol deviations will be identified as major protocol deviations:

- overall IMP compliance less than 80%
- not taking the randomized IMP
- taking prohibited medications

The final definition of major and minor protocol violations will be determined prior to breaking the trial blind.

The number and percentage of subjects with major protocol deviations will be summarized.

9.4 Analysis Sets

Three analysis sets will be defined:

- All randomized analysis set: Includes all randomized subjects

- Intent-to-Treat (ITT) analysis set: Includes all randomized subjects who were assigned to mesalamine 4 g extended release granules in the 000174 trial or randomized via Pathways 2 or 3
- Modified ITT (mITT) analysis set: Includes all subjects who receive at least 1 dose of IMP in the ITT analysis set
- Per protocol (PP) analysis set: Includes all subjects who receive at least 1 dose of IMP and who do not have any of the major protocol deviations in the ITT analysis set
- Safety analysis set: Includes all subjects who receive at least 1 dose of IMP

The assignment of subjects to each analysis set will be finalized prior to breaking the trial blind.

Analyses for the all randomized, ITT, and mITT analysis sets will be conducted according to the randomized treatment. Safety analyses will be conducted according to the treatment actually received rather than according to the treatment assigned.

For each analysis set, the number and percentage of subjects excluded from it will be summarized by the reason for the exclusion.

9.5 Trial Population

9.5.1 Demographics and other Baseline Characteristics

Descriptive statistics of demographics and other baseline characteristics will be presented for all subjects in the ITT, PP, and safety analysis sets by treatment group.

9.5.2 Medical History, Concomitant Medication and Other Safety Evaluations

Medical history will be coded by system organ class (SOC) and preferred term (PT) using the most current version of the Medical Dictionary for Regulatory Activities (MedDRA) available at study initiation and summarized by SOC, PT, and treatment group for the ITT and Safety analysis sets.

Prior and concomitant medications will be coded by the Anatomical Therapeutic Chemical (ATC) classification system and preferred drug name using the World Health Organization Drug Dictionary (WHO-Drug). Prior and concomitant drug usage will be summarized by ATC classification 1st level, ATC classification 2nd level and treatment group for subjects in the ITT and Safety analysis sets.

9.6 Endpoint Assessments

9.6.1 General Considerations

All statistical tests will be conducted at a two-sided 0.05 significance level.

Quantitative variables will be described with the number of non-missing values, mean, standard deviation, median, and minimum/maximum values. Qualitative variables will be described with the

number and percentage of subjects with each qualitative characteristic. Missing values will not be included in the calculation of percentages.

All data will be listed by individual subject and trial visit.

9.6.2 Primary Endpoint

The primary efficacy analysis will be based on the ITT analysis set. The proportion of subjects with remission, defined as rectal bleeding score of 0 and stool frequency score of 0 or 1, with an endoscopic score of 0 or 1 in the Clinical and Endoscopic Response Score at Month 6, will be assessed by the Mantel-Haenszel test stratified by the randomization strata at a two-sided 0.05 significance level. Subjects who discontinue the double-blind regimen before Month 6, as well as subjects with missing remission assessment at Month 6, will be considered not having met the remission criteria. The odds ratio will be estimated and its 95% confidence interval will be provided.

The following sensitivity analyses will be conducted to assess the robustness of the primary analysis:

- as-treated analysis based on actually received treatment
- analysis on the all randomized analysis set
- analysis on the mITT analysis set
- analysis on the PP analysis set
- assessment of the homogeneity of odds ratios across geographical regions, baseline demographic characteristics, and baseline disease characteristics
- analysis on the last observed Clinical and Endoscopic Response Score
- analysis using multiple imputation methods for missing remission assessment at Month 6
- analysis using pattern mixture models for missing remission assessment at Month 6

9.6.3 Secondary Endpoints

Secondary endpoints are the following:

1. The proportion of subjects in clinical remission at Months 2, 4, and 6, defined as a score of 0 for rectal bleeding and 0 or 1 for stool frequency based on Clinical Response Score subset of the Clinical and Endoscopic Response Score
2. Time to relapse, defined as number of days from randomization to the day of withdrawal due to escalation of therapy (i.e., surgical therapy, use of steroids, immunosuppressive or immunomodulating drugs, biologics, increase dose of 5-ASA in any form)
3. The proportion of subjects with an increase from baseline in the Clinical and Endoscopic Response Score by 2 or more points in at least 1 component or by 1 or more points in at least 2 components at Month 6

4. The change from baseline in serum CRP levels at Months 2, 4, and 6
5. The change from baseline in fecal calprotectin levels at Months 2, 4, and 6
6. The change from baseline to each scheduled assessment for published and validated domain scores of the IBDQ
7. Safety assessed by incidence and severity of AEs and abnormal laboratory values

The proportion of subjects in clinical remission at Months 2, 4, and 6 will be analyzed by the generalized estimating equations approach as longitudinal binary outcomes. The model will include randomization strata, treatment, time, and treatment- by-time interaction. The clinical remission rates and odds ratios will be estimated for each time point.

The time to relapse will be analyzed by a log-rank test stratified by the randomization strata.

The change from baseline in serum CRP and fecal calprotectin levels will be assessed with a repeated-measures analysis of covariance (ANCOVA) model that includes randomization strata, treatment, time, and treatment-by-time interaction as fixed effects, and baseline value as a covariate based on the observed data. The adjusted changes from baseline and their difference between treatment groups will be estimated for each time point.

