3 INVESTIGATIONAL PLAN

3.1 Overall Trial Design

3.1.1 Overall Design and Control Methods

This is a randomized, double-blind, placebo-controlled, parallel-group, multicenter, international, Phase 3 trial to investigate the safety and efficacy of therapy with mesalamine 2 g extended release granules (sachet) for maintenance of clinical and endoscopic remission in subjects with UC.

Subjects who are in remission can be enrolled in the current trial via 1 of 3 pathways.

- Pathway 1: Subjects who are in remission following 8 weeks of double-blind treatment in Study 000174 can be randomized into Study 000175. The clinical and endoscopic remission criteria for Study 000174 include a Clinical and Endoscopic Response Score as a score of 0 for rectal bleeding and 0 or 1 with at least 1 point decrease from baseline for stool frequency, with an endoscopic score of 0 or 1.
- Pathway 2: Subjects in remission at the end of the 8-week open-label treatment period in Study 000174 will be allowed to be randomized into Study 000175.
- Pathway 3 – *de novo*: Subjects who did not participate in Study 000174 can also be enrolled; these subjects will have been treated with various medications for UC (excluding biologics and long-term [≥ 6 weeks] immunosuppressants) and will have been in remission for < 1 year. These *de novo* subjects will undergo a 72-hour mesalamine washout prior to entering the current trial and will have a Clinical and Endoscopic Response Score assessment to ensure eligibility. Refer to Section 4.3.1 for a complete listing of restrictions.

All eligible subjects will be randomized during Visit 1/Day 0 (start of maintenance) to 1 of the following treatments:

- one mesalamine 2 g extended release granules (sachet) QD (2 g/day) *OR*
- one 2 g placebo sachet to match mesalamine extended release granules (sachet)

Dose will be administered QD at least 1 hour before or at least 2 hours after a meal at approximately the same time each day. The sachet will be emptied on the tongue and swallowed with at least 8 ounces (240 mL) of water. For all subjects, the first dose of investigational medicinal product (IMP) will be administered the day following randomization/Visit 1.

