4 SELECTION OF TRIAL POPULATION

4.1 Trial Population

4.1.1 Inclusion Criteria

1. Satisfied one of the following criteria for enrollment into the trial:
 - a. Met the remission criteria at Week 8 of Study 000174 (Pathway 1) *or*
 - b. Did not meet the remission criteria during Study 000174 and agreed to an additional 8 weeks of open-label treatment with mesalamine 4 g/day QD, after which met the remission criteria (Pathway 2) *or*
 - c. Subjects not currently enrolled in Study 000174 and currently treated with medications for UC and currently in remission <1 year based on clinical and endoscopic evaluation (rectal bleeding score of 0 and stool frequency scores of 0 or 1, with endoscopic score of 0 or 1 in Clinical and Endoscopic Response Score; i.e., clinical and endoscopic remission). The duration of prior remission must be less <1 year and include a history of flare (defined as escalation of medical therapy[ies]), and/or documented episode of recurrent rectal bleeding accompanied by abdominal pain and increased stool number that required medical intervention) (Pathway 3 – *de novo*)
2. Signed informed consent obtained before any trial-related procedures
3. Male or nonpregnant female subjects aged 18 to 75 years
4. Extent of colonic involvement historically confirmed (i.e., flexible sigmoidoscopy/colonoscopy report, colonoscopy report, biopsy reading) within past 12 months
5. Estimated creatinine clearance ≥ 60 mL/min
6. Females of childbearing potential must agree to use an adequate contraception during the course of the trial. Accepted forms of contraception are: i.e., implants, injectables, hormonal intrauterine device, combined hormonal contraceptives, sexual abstinence, and vasectomized sexual partner. Sterilized or postmenopausal women may also participate. Women must have a negative serum pregnancy test result at screening and negative urine pregnancy test result on baseline/randomization.

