9.6.4 Health-related Quality of Life

Change from baseline to each scheduled assessment will be summarized for published and validated domain scores of the IBDQ. The change from baseline in IBDQ scores will be assessed with a repeated-measures ANCOVA model that includes randomization strata, treatment, time, and treatment-by-time interaction as fixed effects and baseline value as a covariate based on the observed data.

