9.3 Secondary Endpoint(s)

The following key secondary endpoints will be analyzed for the ITT analysis set.

- The proportion of subjects in clinical remission at Months 2, 4, and 6, defined as a score of 0 for both rectal bleeding and stool frequency based on Clinical Response Score subset of the Clinical and Endoscopic Response Score
- Time to relapse, defined as number of days from randomization to the day of withdrawal due to escalation of therapy (i.e., surgical therapy, use of steroids, immunosuppressive or immunomodulating drugs, biologics, increase dose of 5 ASA in any form)

- The proportion of subjects with an increase from baseline in the Clinical and Endoscopic Response Score by 2 or more points in at least 1 component or by 1 or more points in at least 2 components at Month 6
- The change from baseline in serum CRP levels at Months 2, 4, and 6
- The change from baseline in fecal calprotectin levels at Months 2, 4, and 6

The proportion of subjects in clinical remission at Months 2, 4, and 6 will be analyzed by the generalized estimating equations (GEE) approach as longitudinal binary outcomes. The model will include the randomization strata, treatment, time, and treatment- by-time interaction. The clinical remission rates and odds ratio will be estimated for each time point. The overall treatment difference over 6 months will be estimated as the main effect for treatment in the model. The missing values will be imputed as non-remission, and an unstructured working correlation matrix will be used.

The time to relapse will be analyzed by the log-rank test stratified by the randomization strata. If a subject does not have the relapse by Day 168, the time to relapse will be censored at the earlier of the day that the last visit day or Day 168. The hazard ratio of relapse for mesalamine relative to placebo will be estimated (including the 95% CI) using the stratified Cox proportional hazards model with treatment group as a factor and the randomization strata as a stratification variable.

The proportion of subjects with an increase from baseline in the Clinical and Endoscopic Response Score by 2 or more points in at least 1 component or by 1 or more points in at least 2 components at Month 6 will be analyzed using the same statistical method used for the primary efficacy analysis.

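### The GEE for clinical remission omits the entry stool-frequency score (0 or 1), a component of the endpoint; adding it would gain a little power but would not correct a bias

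*Protocol*

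**What the plan says.** - **Model.** Protocol 9.6.3: "The model will include randomization strata, treatment, time, and treatment- by-time interaction". SAP 9.3: "The model will include the randomization strata, treatment, time, and treatment- by-time interaction". SAP 9.3 adds: "The missing values will be imputed as non-remission, and an unstructured working correlation matrix will be used". Rates and odds ratios are to be estimated at each visit.
- **Strata.** Protocol 4.2 stratifies by enrolment pathway and, within Pathway 1, by arm in Study 000174. Stool frequency is not a stratum.
- **Entry scores.** Pathway 3 requires "rectal bleeding score of 0 and stool frequency scores of 0 or 1, with endoscopic score of 0 or 1" (protocol 4.1.1). Pathway 1 requires a "score of 0 for rectal bleeding and 0 or 1 with at least 1 point decrease from baseline for stool frequency" (protocol 3.1.1). Pathway 2 subjects must also meet the remission criteria. The score is established by Visit 1, and SAP 7.1.2 already summarizes it by arm.
- **Endpoint.** Protocol 9.6.3: "defined as a score of 0 for rectal bleeding and 0 or 1 for stool frequency based on Clinical Response Score subset". SAP 2.2.2 agrees. SAP 9.3, where the analysis is specified, instead requires 0 on both scores.
- **Other longitudinal models.** The CRP and calprotectin models use a baseline term: "and baseline value as a covariate based on the observed data. The adjusted changes from baseline". So does the IBDQ model: "treatment-by-time interaction as fixed effects and baseline value as a covariate based on the observed data".

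**The concern.** Clinical remission is built from two scores. Bleeding is 0 at entry for every eligible subject, so only stool frequency varies. Under the protocol definition, on that component, a subject entering at 1 loses remission with a rise of one category, while a subject entering at 0 must rise two. It is therefore plausible, though the documents do not show it, that the entry score predicts the outcome.

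A prognostic baseline score that is already collected usually belongs in the model. Without it, the analysis of the first-listed secondary endpoint may have slightly less power than the data allow. Any chance imbalance between arms in entry stool frequency also passes into the visit-specific odds ratios. What is at stake is efficiency on a secondary endpoint. The primary Mantel-Haenszel test is not affected.

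**Working it through.** **1. Inputs.** From protocol 9.1 and 9.6.1: 120 per arm, 68% versus 49%, two-sided 0.05. Those rates are stated for the primary endpoint and are borrowed here for clinical remission at Month 6, because the documents give no rates for that endpoint. Two inputs are assumed: the share q entering at score 1 (20-50%), and the odds ratio ψ for remission, score 1 versus 0 (1 = not prognostic; main range 0.5 to 0.33).

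**2. The plan's own figure.** The two-proportion test with pooled variance gives 85.2% power at 120 per arm, which reproduces the stated figure of at least 85%. The plan gives no power or precision figure for the GEE.

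**3. Unadjusted odds ratio, one visit.**
- log OR = ln(0.68/0.32) − ln(0.49/0.51) = 0.794, so OR = 2.21
- SE = √[1/(120·0.68·0.32) + 1/(120·0.49·0.51)] = 0.268
- z = 2.97; power = Φ(2.97 − 1.96) = 84.3%

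**4. Adjusted odds ratio.** For each q and ψ, choose the logistic intercept and treatment effect so that the rates averaged over the score remain 49% and 68%. The SE then comes from the information matrix for intercept, treatment and score. Example with q = 35%, ψ = 0.5: placebo rates are 0.55 (score 0) and 0.38 (score 1), and 0.65·0.55 + 0.35·0.38 = 0.49. The adjusted log OR is 0.815 and its SE 0.272.

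The last column compares variances of the risk difference standardized over the score. The unadjusted variance is [0.68·0.32 + 0.49·0.51]/120. The adjusted one replaces each p(1−p) by its average within score levels; the extra term for variation in the risk difference between levels is negligible.

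| q | ψ | log OR | SE | z | z² ratio | Power | Risk-difference variance ratio |
|---|---|---|---|---|---|---|---|
| any | 1 | 0.794 | 0.268 | 2.97 | 1.00 | 84.3% | 1.000 |
| 20% | 0.5 | 0.809 | 0.271 | 2.99 | 1.02 | 84.9% | 0.982 |
| 20% | 0.33 | 0.833 | 0.275 | 3.03 | 1.04 | 85.7% | 0.954 |
| 35% | 0.5 | 0.815 | 0.272 | 3.00 | 1.02 | 85.1% | 0.974 |
| 35% | 0.33 | 0.850 | 0.278 | 3.05 | 1.06 | 86.3% | 0.936 |
| 50% | 0.5 | 0.817 | 0.272 | 3.00 | 1.03 | 85.1% | 0.973 |
| 50% | 0.33 | 0.853 | 0.279 | 3.06 | 1.06 | 86.4% | 0.932 |

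The z² ratio (adjusted over unadjusted) uses unrounded values. Outside the main range, ψ = 0.67 gives power 84.5-84.6%, and ψ = 0.2 gives 87.2-88.5%.

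The SE of the log odds ratio never falls. Power rises because the adjusted odds ratio is conditional on the score and lies further from 1.

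**5. Three-visit check.** GEE fits to simulated data (240 subjects, 300 runs per case, 35% at score 1, strata in both models, exchangeable working correlation) gave these Month 6 means:
- ψ = 1: SE 0.278 and z 3.09, both unchanged.
- ψ about 0.5: SE 0.277 to 0.281, z 2.99 to 3.01.
- ψ about 0.33: SE 0.276 to 0.285, z 2.91 to 2.98.

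The pattern agrees with step 4. The strata in these data were unrelated to stool frequency, and the SAP plans an unstructured matrix.

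**6. Chance imbalance.** The between-arm difference in the share at score 1 has standard deviation √[2q(1−q)/120], which is 0.052 at q = 20% and 0.063 at 40%. A gap above 10 points then occurs in about 5% and 11% of trials. With 30% at score 1 overall, a 10-point gap moves the unadjusted odds ratio from 2.21 to 2.06 or 2.37 (ψ = 0.5), or to 1.98 or 2.47 (ψ = 0.33).

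**The case against.** The strongest case against is that this is a preference rather than a fault.

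- **The model does contain baseline information.** A reader might infer that the GEE has no baseline covariate. Pathway and prior arm are baseline factors, and they may carry some stool-frequency information because Pathway 1 requires a fall in that score. This stands. The gain beyond strata that are correlated with stool frequency has not been measured and could be smaller.
- **The contrast with CRP, calprotectin and IBDQ is weak.** A reader might infer that the plan is inconsistent. Those models analyse change in measures whose baseline varies. Under the protocol definition every eligible subject starts in clinical remission, so the binary endpoint's own baseline is constant. The primary test, the worsening proportion and time to relapse also adjust for strata only. This stands. The case for the covariate rests on the component score, not on consistency.
- **Precision of the reported odds ratio does not improve.** This stands, as step 4 shows. The benefit is power, or variance on the standardized risk scale.
- **Validity is intact.** Randomization protects against bias and type I error inflation, and the unadjusted standard errors already allow for chance imbalance. This stands.

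What survives is narrow: a known component of the endpoint is unused, and using it costs one parameter.

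**Conclusion.** The point holds as an optional efficiency improvement. The planned GEE is valid. Adding entry stool frequency would gain about 2-6% in squared z at Month 6, or roughly 0.5-2 power points, and would reduce the variance of a standardized risk difference by about 2-3% at ψ = 0.5 and 5-7% at ψ = 0.33. These figures rest on an assumed share at score 1, an assumed prognostic strength and rates borrowed from the primary endpoint. If the score is not prognostic, the gain is near zero.

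A reader might go further and conclude that the secondary result will be biased, or that its odds ratios are needlessly imprecise. The documents support neither.

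The firmer problem is next to it. Protocol 9.6.3 and SAP 2.2.2 allow stool frequency 0 or 1 in clinical remission, while SAP 9.3 requires 0. Under the SAP 9.3 wording, a subject entering at 1 is not in remission at baseline, and the entry score would probably matter more. SAP 9.2.2 records that the remission definition changed during the study, so the SAP 9.3 wording may be a remnant, but the text does not say so.

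**What to change.** Before unblinding:

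1. In SAP 9.3, add the baseline stool-frequency score (0 versus 1) to the GEE as a fixed effect, keeping the existing terms, the non-remission rule for missing values and the unstructured working correlation. Align protocol 9.6.3.
2. State a rule for subjects whose baseline score is missing or outside 0-1.
3. Report remission rates and differences by arm at each visit, standardized over the baseline score and strata: predict for every ITT subject under each arm, then average. Name the variance method, for example the delta method with the robust covariance, or a bootstrap by subject.
4. In the same edit, reconcile the clinical-remission definition in SAP 9.3 with SAP 2.2.2 and protocol 9.6.3.

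No new data are needed, because the score is collected for eligibility. The costs are one parameter, a standardization step, and an odds ratio that becomes conditional on entry stool frequency as well as on the strata. Changing protocol 9.6.3 requires an amendment under protocol 12.1. If that is not worthwhile, the model change can be made in the SAP and recorded in SAP section 12, which now states that there is no deviation.
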